8.11 Interim Analysis/Criteria for Stopping Study

After testing the drug on 11 patients in the first stage, the trial will be terminated if 0 respond. If the trial goes on to the second stage, a total of 37 patients will be studied. If the total number responding is less than or equal to 2, the combination is rejected.

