6 STUDY ASSESSMENTS AND PROCEDURES

The following schedule of assessments applies to all subjects (see Section 6.1). More frequent assessments should be obtained if clinically indicated.

CONFIDENTIAL

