6.3.1.8 Disease Assessment

Contrast enhanced imaging studies (CT or MRI) will be performed at screening and every 8 weeks beginning Cycle 3/Day 1. All sites of known disease must be assessed. CT modalities should be done according to standard of care for the subject's disease.

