8.3 Definition of Endpoints

Objective response (radiographic response) rate: proportion of all subjects with confirmed PR or CR according to RECIST 1.1, from the start of treatment until disease progression/recurrence

CONFIDENTIAL

(taking as reference for progressive disease the smallest measurements recorded since the start of treatment)

Disease control rate: proportion of all subjects with stable disease (SD) for 8 weeks, or partial response (PR), or complete response (CR) according to RECIST 1.1, from the start of treatment until disease progression/recurrence (taking as reference for progressive disease the smallest measurements recorded since the start of treatment).

Progression-free survival: a measurement from the date of first treatment until the criteria for disease progression is met as defined by RECIST 1.1 or death occurs. Subjects who have not progressed will be right-censored at the date of the last disease evaluation.

Overall survival (OS): a measurement from the date of first treatment until death from any cause.

Safety: Adverse event terms recorded in the eCRFs defined by the National Cancer Institute (NCI) CTCAE v4.03. Seriousness, severity grade and relationship to study treatment will be assessed by the investigator.

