8.5 Sample Size, Accrual and Study Duration

The optimal two-stage design to test the null hypothesis that $P \leq 0.025$ versus the alternative that $P \geq 0.150$ has an expected sample size of 17.32 and a probability of early termination of 0.757. If the drug is actually not effective, there is a 0.045 probability of concluding that it is (the target for this value was 0.050). If the drug is actually effective, there is a 0.198 probability of

CONFIDENTIAL

concluding that it is not (the target for this value was 0.200). After testing the drug on 11 patients in the first stage, the trial will be terminated if 0 respond. If the trial goes on to the second stage, a total of 37 patients will be studied. If the total number responding is less than or equal to 2, the combination is rejected. To allow for a few patients being not evaluable for efficacy, up to 40 subjects may be enrolled. It is estimated that two patients per month will meet eligibility criteria. As such we estimate 6 months to complete the first cohort and 15 months to complete enrollment to the second cohort. Average follow-up is expected to be 9 months to a year.

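### Does leaving the scan for the stage-1 0-of-11 decision unnamed put the stated 80% power at risk?

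*Combined protocol and SAP*

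**What the plan says.** Section 8.11, the synopsis and section 8.5 give the same stage-1 rule: "After testing the drug on 11 patients in the first stage, the trial will be terminated if 0 respond". Otherwise the trial goes on to 37 patients, and two or fewer responses in total reject the combination.

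Section 8.3 defines the response rate as the "proportion of all subjects with confirmed PR or CR according to RECIST 1.1". Section 8.4.3 limits the efficacy population to treated patients who have been evaluated for the primary endpoint and have no significant protocol violation. Section 6.3.1.8 schedules imaging at screening and then "every 8 weeks beginning Cycle 3/Day 1", which is week 8, week 16 and so on with 28-day cycles. The introduction to section 6 adds: "More frequent assessments should be obtained if clinically indicated".

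Section 8.5 says the design "has an expected sample size of 17.32 and a probability of early termination of 0.757" under the null rate of 2.5%. It gives a type I error of 0.045 and a type II error of 0.198 at a true rate of 15%. Its accrual assumption is two eligible patients per month, from which it derives the timeline: "As such we estimate 6 months to complete the first cohort and 15 months to complete enrollment to the second cohort". Section 9 requires weekly review meetings whose summaries include the responses observed, and section 9.4 keeps subject status current because it may affect enrolment.

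**The concern.** No section names the data cut for the stage-1 decision, a minimum follow-up for the 11th patient, or the status of a PR that has been seen once. Because the endpoint requires confirmation and scans are eight weeks apart, a response at the first scan becomes a confirmed response only at week 16, unless an earlier scan is clinically indicated. A team that applied section 8.3 literally on the day of the 11th patient's first scan would score the last few patients as non-responders before any of them could have been confirmed.

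The accrual estimate seems to invite an early look. Two cohorts of 6 and 15 months make 21 months, while 37 patients at two per month take 18.5. The difference of 2.5 months covers the 11th patient's week-8 scan but not the week-16 scan.

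A single response decides stage 1 of an open-label, single-arm trial. If the cut were settled after the scans had been seen, the choice could depend on the data, and the stated error rates would hold under only one reading. At stake would be abandoning a combination that meets the 15% target.

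**Working it through.** **Inputs.** From section 8.5: p0 = 0.025, p1 = 0.15, stop at 0 of 11, reject at 2 or fewer of 37, two patients per month. From section 6.3.1.8: scans at week 8 and every 8 weeks after. From section 8.3: confirmed response. Assumptions: evenly spaced enrolment at months 0, 0.5, …, 5.0 for the first 11, every responder in PR at week 8, and confirmation at week 16. Months convert to weeks by 30.4375/7.

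**The plan's figures, with the status of all 11 known.**
- Early termination under H0: 0.975^11 = 0.7569.
- Expected size under H0: 11 + (1 − 0.7569) × 26 = 17.32.
- Type I error: P(X37 ≥ 3) − 0.7569 × P(X26 ≥ 3) = 0.0647 − 0.7569 × 0.02645 = 0.0447.
- Power: P(X37 ≥ 3) − 0.85^11 × P(X26 ≥ 3) = 0.9308 − 0.1673 × 0.7704 = 0.8019, so the type II error is 0.198.

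All four match section 8.5.

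**The early, confirmed-only look.** When patient 11 reaches week 8, patient i has been on study for 8 + (11 − i) × 0.5 × 30.4375/7 weeks. Patient 7 is at 16.7 weeks and patient 8 at 14.5, so m = 7 of the 11 have had a week-16 scan. With m countable patients, the false-stop probability at 15% is 0.85^m, and power is 0.9308 − 0.85^m × P(X(37−m) ≥ 3).

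| Look, counted from entry of patient 11 | m | False stop | Power |
|---|---|---|---|
| week 8 | 7 | 0.321 | 0.9308 − 0.3206 × 0.8486 = 0.659 |
| 10.9 weeks | 8 | 0.272 | 0.9308 − 0.2725 × 0.8316 = 0.704 |
| 13.0 weeks | 9 | 0.232 | 0.9308 − 0.2316 × 0.8129 = 0.743 |
| week 16 | 11 | 0.167 | 0.802 |

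The type I error at m = 7 is 0.0647 − 0.8376 × 0.03839 = 0.033, so the early look is conservative under the null.

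**Where the loss lies.** The excess false stop at week 8 is 0.85^7 − 0.85^11 = 0.3206 − 0.1673 = 0.153. It factors as 0.85^7 × (1 − 0.85^4): no response among patients 1 to 7 and at least one among patients 8 to 11. Under these assumptions all 11 have had their week-8 scan by then, so each of these trials has a PR on record that is waiting for its second scan. If no PR is visible, the stopping probability is the design's own 0.167.

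**The timeline.** 21 − 37/2 = 2.5 months, or 10.9 weeks. On the enrolment grid used above, however, patient 37 enters at 36 × 0.5 = 18.0 months. That leaves 3.0 months, or 13.0 weeks. The inferred slack moves by two weeks with the counting convention, and the inputs are rounded estimates.

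**If an unconfirmed PR were allowed to count.** Let u be the share of patients with a PR that is never confirmed; the documents give no value. Early termination under H0 becomes (0.975 − u)^11, and the type I error is 0.0647 − (0.975 − u)^11 × 0.02645. At u = 0.025 these are 0.569 and 0.050, with an expected size of 11 + 26 × (1 − 0.569) = 22.2. At u = 0.05 they are 0.424 and 0.053 (0.0535 before rounding), with an expected size of 26.0. The type I error passes 0.05 only when u exceeds about 0.027, so never-confirmed PRs would have to outnumber true responders under the null.

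**The case for a change.** The strongest case for a change is that the omission is real and its consequence can be computed from the plan's own accrual rate and scan schedule. Section 8.11 neither cites section 8.3 nor says what to do with a pending PR, and weekly review does not define what counts at the decision. A few sentences would settle it without an added patient or scan.

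The omission stands, and so does the arithmetic. The power loss does not, as a property of this plan. It pairs the strictest endpoint with the earliest possible cut, and no section prescribes that pair. Section 8.3 already answers most of the question about unconfirmed responses. Section 8.4.3 asks that patients have been evaluated for the primary endpoint, and a patient whose PR awaits confirmation is not a known non-responder.

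A limited point survives. If some responders first respond after week 8, closing at that scan with no PR in sight would also cost power: 0.773 if an assumed 80% of responders show a PR at the first scan and the rest at later scans. That argues for judgement about follow-up. A fixed cut-off is not free either. Treating stable disease at week 16 as non-response for stage 1 would bring power to 0.79 or 0.77 if an assumed 5% or 10% of responders appear later, and it would narrow section 8.3's window, which runs until progression.

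**Conclusion.** The concern does not call for a change. Section 8.11 leaves the data cut unnamed, but its rule, read with sections 8.3 and 8.4.3, needs the response status of all 11 patients, and on that basis 0.802, 0.045, 0.757 and 17.32 are all correct. The fall to 0.659 requires terminating the trial at the 11th patient's week-8 scan with a PR in hand and unconfirmed. The weekly review of responses would show that PR, and no sensible team would close the trial on it.

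The 0.659 rests on even accrual of two per month, all responders in PR by week 8, and confirmation only at the next scheduled scan. The inflated type I error rests on an assumed never-confirmed rate with no source in the documents, and the timeline is too coarse to show which scan was intended. If accrual simply continued during an 8- to 16-week wait, the expected size under the null would rise to 20.1 to 22.9 at two per month, with type I error and power unchanged. What remains is operational detail that can be filled in correctly under the existing text.

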9 DATA AND SAFETY MONITORING

This study will be conducted in accordance with the IU Simon Cancer Center Institutional DSMP for **High Risk Trials**. Investigators will conduct continuous review of data and subject safety. Weekly review meetings for high risk trials are required and will include the principal investigator, clinical research specialist and/or research nurse (other members per principal investigator's discretion). Weekly meeting summaries should include review of data and subject safety by including for each dose level: the number of subjects, significant toxicities as described in the protocol, dose adjustments and responses observed. Study teams should maintain meeting minutes and attendance for submission to the DSMC upon request.

9.1 Data and Safety Monitoring Committee

The IUSCC Data and Safety Monitoring Committee (DSMC) is responsible for oversight of subject safety, regulatory compliance, and data integrity for this trial. The DSMC will review this study semi-annually to review overall trial progress, toxicity, compliance, data integrity, and accrual per the Institutional DSMP.

Furthermore, the DSMC conducts an administrative review of serious adverse events (SAEs), deviations, reportable events, and any other outstanding business. Major issues may require further DSMC review or action.

For any increase in frequency of grade 3 or above adverse events (above the rate reported in the Investigator Brochure or package insert), the principal investigator will notify the DSMC Chair immediately. The notification will include the incidence of study adverse events, grades, and attributions, as well as investigator statements regarding comparison with risks per the IB/ package insert.

At any time during the conduct of the trial, if it is the opinion of the investigators that the risks (or benefits) to the subject warrant early closure of the study, the DSMC Chair and Compliance Officer must be notified within 1 business day via email, and the IRB must be notified within 5 business days. Alternatively, the DSMC may initiate suspension or early closure of the study based on its review

CONFIDENTIAL

9.2 IND Annual Reports

For trials with an IND held locally by the IU principal investigator or university, the IND Annual Report will be reviewed by the DSMC.

9.3 Study Auditing and Monitoring

All trials conducted at the IUSCC are subject to auditing and/or monitoring per the Institutional DSMP. Reports will be reviewed by the full DSMC at the time of study review.

9.4 Oncore Reporting Requirements

The DSMC reviews data and study progress directly from Oncore; therefore, timely data entry and status updates are vital. Study data must be entered within Oncore promptly, no later than one week from study visit occurrence. Subject status in Oncore will be updated in real time, as this may affect overall trial enrollment status. Global SAEs and deviations will be reviewed on a monthly basis by the DSMC Chair directly from Oncore.

9.5 Study Accrual Oversight

Accrual data will be entered into the IU Simon Cancer Center OnCore system. The Protocol Progress Committee (PPC) reviews study accrual twice per year, while the PPC coordinator reviews accrual quarterly.

9.6 Oncore Safety Reporting

In addition to protocol- and regulatory-required safety reporting, all serious adverse events (SAEs) will be captured in the Oncore system within 1 business day of notification. Initial SAE reporting will include as much detail as available, with follow-up to provide complete information.

Attributions will be assessed to study drugs, procedures, study disease, and other alternate etiology.

9.7 Protocol Deviation Reporting

Protocol deviations will be entered into OnCore within 5 days of discovery and reviewed by the DSMC Chair on a monthly basis. Findings will be reported to the full DSMC at the time of study review. For serious or repetitive protocol deviations, additional action may be required by the DSMC.

CONFIDENTIAL

10 ETHICAL ASPECTS

10.1 Local Regulations

The study must fully adhere to the principles outlined in “Guideline for Good Clinical Practice” (GCP) ICH E6 Tripartite Guideline (January 1997). The investigator will ensure that the conduct of the study complies with the basic principles of GCP as outlined in the current version of 21 Code of Federal Regulations, subpart D, Part 312, “Responsibilities of Sponsors and Investigators” Part 50, “Protection of Human Subjects” and Part 56, “Institutional Review Boards.”

10.2 Informed Consent

The site investigator will ensure the subject is given full and adequate oral and written information about the nature, purpose, possible risks and benefits of the study. Subjects must also be notified they are free to discontinue from the study at any time. The subject should be given the opportunity to ask questions and allowed time to consider the information provided.

The subject’s signed and dated informed consent must be obtained before conducting any procedure specifically for the study. The site investigator must store the original, signed informed consent form. A copy of the signed informed consent form must be given to the subject.

The CRF for this study contains a section for documenting informed subject consent, and this must be completed appropriately. If new safety information results in significant changes in the risk/benefit assessment, the consent form should be reviewed and updated as necessary. All subjects (including those already being treated) should be informed of the new information, should be given a copy of the revised form, and should give their consent to continue in the study.

10.3 Institutional Review Board/Ethics Committee

This study is being conducted under a United States Investigational New Drug application or other Clinical Trial Application, as appropriate. This protocol (and any modifications) and appropriate consent procedures must be reviewed and approved by an IRB/EC. This board must operate in accordance with current local, regional, and federal regulations. The investigator will send a letter or certificate of IRB/EC approval to Exelixis (or designee) before subject enrollment and whenever subsequent modifications to the protocol are made.

CONFIDENTIAL

10.4 Compliance with Trial Registration and Results Posting Requirements

Under the terms of the Food and Drug Administration Modernization Act (FDAMA) and the Food and Drug Administration Amendments Act (FDAAA), the sponsor-investigator of the trial is solely responsible for determining whether the trial and its results are subject to the requirements for submission to the Clinical Trials Data Bank, <http://www.clinicaltrials.gov>. The sponsor-investigator has delegated responsibility to IUSCC Clinical Trials Office for registering the trial and posting the results on [clinicaltrials.gov](http://www.clinicaltrials.gov). Information posted will allow subjects to identify potentially appropriate trials for their disease conditions and pursue participation by calling a central contact number for further information on appropriate trial locations and study site contact information.

10.5 Future Use of Subject Samples

. Samples that are being collected for research purposes will be used for this study, and they will not be banked for use on future, yet undetermined studies.

11 CONDITIONS FOR MODIFYING THE PROTOCOL

11.1 Emergency Modifications

The sponsor-investigator may implement a deviation from, or a change of, the protocol to eliminate an immediate hazard(s) to trial subjects without prior IRB approval. As soon as possible after the modification has been made, the implemented deviation or change and the reasons for it should be submitted to the IRB for review and approval.

11.2 Other Protocol Deviations/Violations

If a deviation or violation occurs, the deviation should be reported in OnCore[®]. Any protocol violation that occurs must be reported to the IRB per institutional policies and reported to IUSCC as soon as possible. IUSCC will determine if the violation affects the safety of the study subject and integrity of the data.

11.3 Amendments

If it is necessary for the study protocol to be amended, the amended protocol will be generated by IUSCC and must be approved by the FDA (if applicable) and the IRB prior to implementation. Local requirements must be followed.

The Principal Investigator is responsible for the distribution of these documents to the IRB, and to the study's research staff. The distribution of these documents to the regulatory authority will be handled according to local practice.

CONFIDENTIAL

12 CONDITIONS FOR TERMINATING THE STUDY

Exelixis reserves the right to terminate the study, and investigators reserve the right to terminate their participation in the study, at any time. Should this be necessary, Exelixis and the investigator will arrange the procedures on an individual study basis after review and consultation. In terminating the study, Exelixis and the investigator will ensure that adequate consideration is given to the protection of the subjects' interests.

13 STUDY DOCUMENTATION AND RECORD KEEPING

13.1 Investigator's Files and Retention of Documents

The investigator must maintain adequate and accurate records to enable the conduct of the study to be fully documented and the study data to be subsequently verified. These documents should be classified into two separate categories as follows: (1) the investigator's study file, and (2) subjects' clinical source documents.

The investigator's study file will contain the protocol and protocol amendments, CRFs, query forms, IRB/EC and governmental approvals with correspondence, sample informed consent, drug records, staff curriculum vitae and authorization forms, and other appropriate documents and correspondence.

Subjects' clinical source documents include the subjects' hospital/clinic records; physicians' and nurses' notes; the appointment book; original laboratory, ECG, electroencephalogram, X-ray, pathology and special assessment reports; signed informed consent forms; consultant letters; and subject screening and enrollment logs.

The investigator must keep these two categories of documents on file for at least the latest of 2 years following the marketing application approval date for the study treatment in the indication being investigated, 2 years after the investigation is completed or discontinued, or for a time consistent with local regulatory requirements. After that period, the documents may be destroyed subject to local regulations with prior written permission from Exelixis. If the investigator wants to assign the study records to another party or move them to another location, Exelixis must be notified in advance.

If the investigator cannot guarantee the archiving requirement at the study site for any or all of the documents, special arrangements must be made between the investigator and Exelixis to store these in a sealed container outside of the study site so that they can be returned sealed to the

CONFIDENTIAL

investigator in case of a regulatory audit. When source documents are required for the continued care of the subject, appropriate copies should be made for storing outside of the study site.

13.2 Source Documents and Background Data

Upon request, the investigator will supply its licensees and collaborators with any required background data from the study documentation or clinic records. This is particularly important when CRFs are illegible or when errors in data transcription are suspected. In case of special problems or governmental queries or requests for audit inspections, it is also necessary to have access to the complete study records, provided that subject confidentiality is protected.

13.3 Audits and Inspections

The investigator should understand that source documents for this study should be made available, after appropriate notification, to qualified personnel from the Exelixis Quality Assurance Unit (or designee) or to health authority inspectors. The verification of the CRF data must be by direct inspection of source documents.

13.4 Case Report Forms and Data Submission

This study will utilize electronic Case Report Form completion in the OnCore® database. A calendar of events and required forms are available in OnCore® at <https://cancer.iu.edu/oncore>. The OnCore® database is a comprehensive database used by the Indiana University Simon Cancer Center (IUSCC) Clinical Trials Office (CTO) and supported by the Indiana University Simon Cancer Center. Access to data through OnCore® is restricted by user accounts and assigned roles. Once logged into the OnCore® system with a user ID and password, OnCore® defines roles for each user which limits access to appropriate data.

All source documents are to remain in the patient's clinic file. All documents should be kept according to applicable federal guidelines. Clinical trial data in OnCore® are periodically monitored by the IUSCC per the Data Safety Monitoring Committee (DSMC) Charter (see Section 9.1.1).

All paper forms should be typed or filled out using indelible ink and must be legible. Errors should be crossed out but not obliterated, the correction inserted, and the change initialed and dated by the investigator or his or her authorized delegate.

The investigator should ensure the accuracy, completeness, legibility, and timeliness of the data in the CRFs and in all required reports.

CONFIDENTIAL

